 - ii) CR The trial will stop accrual if the number of patients who achieve CR is <1/10 or 4/20.

If the study completes full accrual, we will declare this regimen not of further interest if either the OS6 rate is $\leq 19/30$ or if $\leq 7/30$ achieve CR.

The maximum sample size will be 30. We see approximately 90 patients older than 60 with newly-diagnosed AML annually. This trial will replace protocol 2566. While there will be competing trials, 2566 accrued 30 patients in 1 year and we anticipate that this study will have similar accrual. Enrollment would begin once IRB approval is secured. We believe it important to monitor both survival and CR. Although historically it has been thought that there was a tight link between survival and CR, more recent evidence does not support this assumption. In particular, studies by the MRC/NCRI group in the UK indicate that CR rates can increase without effect on overall survival (OS), with OS the most important outcome for the patient. Hence we do not require an **improvement** in CR rate. However, data from SWOG and MD Anderson indicate that with therapy similar to what we are testing in this protocol, the great majority of long-term survivors (alive for > 2 years after starting therapy) achieve CR. Given this background, we are unwilling to accept a **decline** in CR rate.

d) Performance of the design under various clinical scenarios

Assuming independence between OS6 and CR, we simulated the operating characteristics of the design and summarize results in the table below. In reality, OS6 and CR may not be independent, but we believe this is a conservative assumption for evaluating properties of the design.

The design's operating characteristics in are shown below:

Scenario	Probability stop after 10 patients	Probability stop after 20 patients	Probability stop early	Probability positive trial
Alternative, no decrease in CR OS6 = 80% CR = 45%	6%	3%	9%	90%
Alternative with improved CR OS6 = 80% CR=60%	4%	2%	5%	94%
Null, decrease in CR OS6 = 65% CR = 25%	42%	28%	71%	17%
Null, no decrease in CR OS6 = 65%	27%	20%	47%	41%

CR = 45%				
Too toxic, worse OS and no decrease in CR	62%	26%	89%	4%
OS6 = 50% CR = 45%				

If OS6 is improved and the CR rate is the same as the historical rate, this design has 90% power. If both OS6 and the CR rates are improved, this design has 94% power. If OS6 is not improved and the CR rate is worse than the historical rate, the probability of incorrectly concluding the trial is positive and the regimen warrants further study is 17%. If OS6 is not improved and the CR rate is the same as the historical rate, the probability of incorrectly concluding the trial is positive and the regimen warrants further study is 41%. If the OS6 is worse than the historical rate and the CR rate is the same as the historical rate, the probability trial incorrectly has a positive result is 4% and the probability of stopping accrual early is 89%.

Regulatory and Reporting Requirements

Adverse Event Reporting

Many, if not most of the patients to be treated here, would presumably receive anthracycline + ara-C, for example as in "3+7". Expectations for grade 3-4 organ toxicity with idarubicin + ara-C have been reported (see Table 1 below).(22) We will use these as a control for our 10-day decitabine + 10-day ara-C regimen.

Grade ≥3 adverse events other than hematologic toxicities will be recorded, graded, and reported as appropriate. AEs will be collected for the duration that the patients remain on protocol. AEs that do not meet the requirement for expedited reporting will be reported to the IRB as part of the annual renewal of the protocol. Myelosuppression and associated complications are expected events during leukemia therapy; therefore, myelosuppression and associated simple complications such as fever, infections, bleeding, and related hospitalizations will not be reported as individual AEs but will be summarized in the annual report to the IRB.

Toxicities will be graded using the CTCAE (NCI Common Terminology Criteria for Adverse Events) Version 4.03. Information on these criteria can be downloaded from the CTEP web site (http://ctep.cancer.gov/reporting/ctc.html).

Grade 3-4 toxicity expectations

Table 1 Percent Grade 3-4 toxicity expectations with Idarubicin + Cytarabine (21) Toxicity Percent of Patients Affected (%)

Anemia 67

Thrombocytopenia 70

Neutropenia 94

Fever of Unknown Origin 31

Documented Infection 61

Hospitalization 92

Renal 2

Hepatic 22

Cardiac 4

Dialysis 6

Intensive Care Unit Admission 27

Mechanical Ventilation 14

Hyponatremia 14

Hypokalemia 38

Data and Safety Monitoring Plan

Ongoing trial oversight is carried out by the Principal Investigator and the research staff. They will meet frequently to review recently acquired data and adverse events. The data recorded within the research charts and protocol database will be compared with the data that is available from the medical record and/or clinical histories. All investigators on the protocol have received formal training in the ethical conduct of human research. The Principal Investigator will receive monitoring support as described below. Institutional support of trial monitoring is provided in accordance with the FHCRC/University of Washington Cancer Consortium Institutional Data and Safety Monitoring Plan. Under the provisions of this plan, FHCRC Clinical Research Support coordinates data and compliance monitoring conducted by consultants, contract research organizations, or FHCRC employees unaffiliated with the conduct of the study. Independent monitoring visits occur at specified intervals determined by the assessed risk level of the study and the findings of previous visits per the institutional DSMP. In addition, protocols are reviewed at least annually and as needed by the Consortium Data and Safety Monitoring Committee (DSMC), FHCRC Scientific Review Committee (SRC), and the FHCRC/University of Washington Cancer Consortium Institutional Review Board (IRB). The review committees evaluate accrual, adverse events, stopping rules, and adherence to the applicable data and safety monitoring plan for studies actively enrolling or treating patients. The IRB reviews the study progress and safety information to asses continued acceptability of the risk-benefit ratio for human subjects. Approval of committees as applicable is necessary to continue the study. The trial will comply with the standard guidelines set forth by these regulatory committees and other institutional, state and federal guidelines.

Data Management/Confidentiality

The investigator will ensure that data collected conform to all established guidelines. Each patient is assigned a unique patient number to assure confidentiality. Patients will not be referred to by this number, by name, or by any other identifier in any publication or external presentation. The licensed medical records department, affiliated with the

IRB Approved
Document Release Date: 03/22/2017

9019

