- d.) Patients may have received azacitidine, decitabine, or lenalidomide but no "cytotoxic therapy" such as ara-C or anthracyclines. Data suggest that failure to respond to azacitidine reduces probability of response to 3+7(19). Hence in the interest of having a relatively homogeneous population, while patients who have received and failed azacitidine or decitabine will be eligible for this study, they will be analyzed separately from patients who have not received these drugs.
- e.) Treatment related mortality (TRM) score < 22.9 (18). Patients with TRM scores > 13.1, in whom the risk of death within 28 days of beginning induction therapy has averaged 41%, will preferentially be placed on protocol 2642.
- f.) Provision of written informed consent
- g.) Note, unlike pharmaceutical company sponsored protocols eligibility is not conditioned on bilirubin, creatinine, or absence of other malignancy within the past 2-3 years. The TRM score incorporates creatinine and thus a high creatinine

can in principle be offset by favorable values for the other covariates in the TRM score (20). Bilirubin was not a covariate in the TRM. Furthermore, in the doses we are using, dose adjustment of decitabine or ara-C is not indicated in the presence of renal or hepatic abnormalities. Our broad eligibility criteria may increase the likelihood that our results will be generalizable. The inability to reproduce results of early phase AML studies has been a problem in the past (21).

4. Pre-treatment Evaluation

The following is a recommendation and will be collected from standard of care evaluations; missing items will not be considered a protocol deviation.

- a.) CBC, differential, platelet count
- b.) Chemistry to include bilirubin, ALT, AST, albumin, BUN, creatinine, electrolytes including calcium and magnesium
- c.) If not done within the previous 30 days bone marrow for morphology, flow, cytogenetics, FISH, and, with insurance approval, ONCOPLEX

5. Treatment Plan

The following is a recommendation and will be collected from standard of care evaluations; variations to the schedule will be done with physician discretion and will not be considered a protocol deviation.

- a.) Decitabine 20 mg/m2 daily IV days 1 through 10
- b.) Ara-C 100 mg/m2 once daily by IV bolus days 1 through 7
- c.) Patients will receive 2 such courses given 28-35 days apart regardless of blood counts.

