- d.) On course 1 hydroxyurea will be given if the blast count (WBC X % blasts) either remains > 50,000 for 3 days after beginning decitabine+ ara-C or reaches this level after therapy is begun. Patients will be removed from study if hydroxyurea is still required more than 3 weeks after therapy is begun
- e.) Bone marrow will be examined 4-5 weeks after initiation of course 2, with decisions based on the result of this marrow and on assessment of non-hematologic toxicity on courses 1 and 2.
- f.) Patients will be re-evaluated after any 3rd course

Marrow response after course 2	Non hematologic toxicity	Plan
< 5% blasts (flow)	< grade 3	Course3 at same doses (dec 20 mg/m2 days 1-10, ara-C 100 mg/m2 days 1-7)
>19% blasts (flow)	< grade 3	Course 3 at same dose decitabine, but ara-C at 1 g/m2 daily X5 (days 1-5)

9019

7017		
5-19% blasts	<grade3< th="">Doctor decides	</grade3<>	Doctor decides
(flow)		between the 2 ara-
		C doses; reasons for
		decision elicited

<5% blasts	>grade 2	Course 3 at same
(flow)		doses as courses 1
		and 2, but duration
		shortened to
		decitabine days 1-8
		and ara-C days 1-5.
>4% blasts	>grade2	Off study
(flow)		

Response after course 3	Non hematologic toxicity	Plan
CR, CRp, CRi	< grade 3	1-2 more courses at same dose as course 3
	>grade 2	1-2 more courses at 20-50 % dose decreases
None of above	N/A	Off study

CR = < 5% marrow blasts (by morphology), ANC > 1000, platelet count > 100,000

CRp = as for CR but with platelet count < 100,000

CRi = <5% marrow blasts by morphology and either (a) marrow cellularity $\ge 15\%$, (b) at least 200 cells counted, or (c) ANC 500-1,000

6.) Post-treatment Testing

The following is a recommendation and will be collected form standard of care evaluations; missing items will not be considered a protocol deviation.

- a.) CBC, differential, platelets at least twice weekly
- b.) Electrolytes, BUN, creatinine at least weekly
- c.) Bone marrow exam after 2 cycles of therapy, as described above
- d.) If patient has 5-19% blasts by flow note reasons for decision to keep ara-C dose as on courses 1-2 or to increase it (see from below)

7.) Criteria For Removal From Study

- a.) Requirement for hydroxyurea to keep WBC < 50,000 more than 3 weeks after beginning treatment (see E4. above)
- b.) > grade 2 non-hematologic toxicity and > 4% blasts (by flow) after course 2
- c.) No CR, CRp, CRi after course 3
- d.) Physician's or patient's decision

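### Independence of OS6 and CR is called conservative without limit; under positive dependence that is true for power but not for the false-positive rates, and only the 17% figure moves materially

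*Combined protocol and SAP*

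**What the plan says.** Section 8(d) introduces its table with "Assuming independence between OS6 and CR, we simulated the operating characteristics of the design". It then accepts that the endpoints may in fact be dependent, but says of independence that "we believe this is a conservative assumption for evaluating properties of the design". Nothing restricts this to power, and no run under dependence is reported.

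The table and the paragraph after it give three kinds of property:

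- power: 90% and 94%;
- the probability of a wrongly positive trial: 17%, 41% and 4%;
- the probability of stopping early.

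For OS6 65% with CR 25%, the text states that "the probability of incorrectly concluding the trial is positive and the regimen warrants further study is 17"%.

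On the link between the endpoints, Section 8(c) points both ways. Of the older view that CR and survival are tightly linked, it says "more recent evidence does not support this assumption". It also says that with similar therapy "the great majority of long-term survivors (alive for > 2 years after starting therapy) achieve CR". Neither statement gives a correlation between CR and survival at 6 months.

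**The concern.** Under Section 8(c) the regimen is dropped if either endpoint falls short, so a positive result requires both to pass. With the two marginal rates held fixed, the sign of the dependence moves the probability of passing both in the same direction in every scenario. Where the regimen works, a higher probability is more power. Where it does not, a higher probability is more false positives. Whichever sign applies, independence cannot be conservative for both.

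The schedule supplies one reason to expect positive dependence. Section 5(c) says "Patients will receive 2 such courses given 28-35 days apart regardless of blood counts" and Section 5(e) says "Bone marrow will be examined 4-5 weeks after initiation of course 2". The first planned response marrow therefore falls at about 4 + 4 = 8 to 5 + 5 = 10 weeks. A patient who dies before it fails both endpoints.

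The table is the plan's evidence on error control, and a reader could take the word conservative to mean that 17% is a ceiling. Under positive dependence it is not. The row concerned is the one in which the regimen neither improves survival nor maintains the CR rate.

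**Working it through.** **Inputs (Sections 8(c) and 8(d)).** Looks at 10 and 20 patients, maximum 30. Stop if OS6 ≤5/10 or ≤12/20. Positive if OS6 ≥20/30 and CR ≥8/30, the complement of the printed final rule. The CR stopping rule is printed as <1/10 or 4/20. I used ≤1/10 and ≤4/20, the only reading tried that comes close to the printed 65%/25% row:

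| CR stopping rule | Stop at 10 | Stop at 20 | Positive |
|---|---|---|---|
| Printed table | 42% | 28% | 17% |
| ≤1/10 and ≤4/20 | 43.2% | 26.9% | 17.3% |
| <1/10 and ≤4/20 | 29.1% | 38.7% | 18.3% |
| <1/10 and <4/20 | 29.1% | 28.6% | 20.1% |

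**Method.** Exact enumeration in three blocks of 10. Each patient falls in one of four cells (alive or not, CR or not) with

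P(alive and CR) = p_OS·p_CR + φ·√[p_OS(1−p_OS)·p_CR(1−p_CR)],

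which cannot exceed min(p_OS, p_CR). The marginal rates stay fixed.

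**Step 1: reproduce the plan (φ = 0).** The probability of a positive trial is 90.0, 93.6, 17.3, 41.0 and 3.6%, against the printed 90, 94, 17, 41 and 4%. Early stopping is 8.6, 5.4, 70.1, 46.5 and 88.8%, against 9, 5, 71, 47 and 89%.

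**Step 2: the 65%/25% row under dependence.** Under independence, P(alive and CR) = 0.65 × 0.25 = 0.1625. The square-root term is √(0.65 × 0.35 × 0.25 × 0.75) = 0.2065. The maximum joint probability is 0.25, so the largest φ is (0.25 − 0.1625)/0.2065 = 0.42.

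For early deaths alone, let a share q fail both endpoints and the rest be independent. Then P(alive and CR) = 0.1625/(1 − q). The TRM appendix gives 5% below score 13.11 and 6% below 22.81, and Section 3(e) requires "Treatment related mortality (TRM) score < 22.9". So q = 5% gives 0.1711 (φ = 0.04) and q = 6% gives 0.1729 (φ = 0.05).

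| Dependence | Positive | Stop early |
|---|---|---|
| φ = −0.1 (assumed) | 15.8% | 71.7% |
| Independence | 17.3% | 70.1% |
| Early deaths only, q = 5% | 17.9% | 69.5% |
| Early deaths only, q = 6% | 18.0% | 69.4% |
| φ = 0.1 (assumed) | 18.7% | 68.6% |
| φ = 0.3 (assumed) | 21.8% | 65.4% |
| Bound, φ = 0.42 | 23.8% | 63.3% |

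**Step 3: the other rows, independence to bound.**

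| OS6 / CR | Positive | Stop early |
|---|---|---|
| 80% / 45% | 90.0% → 90.8% | 8.6% → 7.9% |
| 80% / 60% | 93.6% → 93.7% | 5.4% → 5.3% |
| 65% / 45% | 41.0% → 42.5% | 46.5% → 44.9% |
| 50% / 45% | 3.6% → 3.8% | 88.8% → 88.4% |

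**Why only one row moves.** At CR 45% or 60% the CR rules alone are passed with probability 96% or more, so OS6 decides the outcome. At 65%/25% both bind: OS6 alone passes with probability 42.7% and CR alone with 40.4%. Their product is 0.427 × 0.404 = 17.3%.

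**Step 4: sensitivity to the CR rule.** With <1/10 read literally (and ≤4/20), the 65%/25% row is 18.3% under independence, 19.1% at q = 6% and 24.9% at the bound. The direction is the same.

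**The case against.** The strongest reply concerns size. The only dependence that can be tied to figures in the documents is early death, and it moves 17.3% by about 0.7 points. That is less than the gap between the printed table and exact values in places (stop at 10 in this row: 42% printed, 43.2% exact). The φ values of 0.1 and 0.3 are assumptions, and the bound needs every CR patient to be alive at 6 months. Section 8(c) itself argues against a tight link, and its one statement in favour concerns survival beyond 2 years. The TRM figures are 28-day rates from the score's source cohort, not from this regimen, and Section 5 makes the schedule a recommendation. The plan labels the table as assuming independence and words the rest as a belief. It also openly prints a larger 41% false-positive figure, which hardly changes. On this view one limiting clause is enough.

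Most of this stands as a limit on size. Deaths up to weeks 8–10 would exceed the 28-day rates by an amount that is not given, but even an assumed 15% share gives only 19.3%. None of it rescues the wording. Disclosing the assumption is not the same as stating correctly which way it errs, and the stated direction cannot hold for both power and false positives. The evidence that Section 8(c) cites against a tight link says that CR rates can rise without an effect on survival. That is a statement about trial-level effects and does not establish independence within a patient.

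**Conclusion.** The concern holds, as a minor correction to a stated property. It is not an arithmetic error, because 17% is right under independence. Under positive dependence, independence is conservative for power and for wrongful early stopping in the two alternative rows. It is anti-conservative for false positives and for early stopping in the null and toxic rows.

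The material effect is confined to OS6 65%/CR 25%: from 17.3% to about 18% on early deaths alone, 18.7% to 21.8% for assumed φ of 0.1 to 0.3, and at most 23.8%. Power changes by at most 0.8 points. The direction is certain given the sign of the dependence. The sign is plausible but not established by the documents, and the strength is not given at all. With negative dependence (φ = −0.1) the row falls to 15.8% and the word would be right for that row, though then wrong for power. The plan sets no type I error target, and no boundary or sample size rests on this figure.

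**What to change.** Replace the sentence in Section 8(d) with one that limits the claim, for example:

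> If OS6 and CR are positively dependent, these figures are conservative for power and for early stopping under the alternative scenarios; false-positive probabilities would be higher, and early stopping under the null and toxic scenarios lower, than shown.

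Keep the existing figures, labelled as computed under independence. Add sensitivity rows for OS6 65%/CR 25% with the two endpoints generated jointly and the marginal rates unchanged: a stated assumed dependence (for example φ = 0.1 and 0.3), marked as assumed, and the bound, marked as an extreme. State the CR stopping boundary used for these rows, because the bound depends on it: about 24% with ≤1/10 and about 25% with <1/10.

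The cost is one reworded sentence and a short rerun. Sample size and stopping boundaries stay as they are.

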APPENDIX: Treatment-Related Mortality (TRM) Score

Calculation of Simplified Treatment-Related Mortality (TRM) Score

Includes covariates: performance status (PS), age, platelet count, albumin, secondary AML, white blood cell count (WBC), peripheral blood blast percentage, and creatinine.

Score = $100/(1+e^{(-x)})$, with x = -4.08 + 0.89*PS + 0.03*age - 0.008*platelet count - 0.48*albumin + 0.47*(have secondary AML) + 0.007*WBC-0.007*(peripheral blood blast percentage) + 0.34*creatinine

Probability of TRM Above and Below Various Simplified TRM Score Cut-offs

TRM Score Interval	Patients below/ within/above TRM Score Interval (%)	TRM Probability if below TRM Score Interval (%)	TRM Probability if within TRM Score Interval (%)	TRM Probability if above TRM Score Interval (%)
0 - 1.9	0/20/80	=	1	12
1.91 - 3.9	20/20/60	1	2	16
3.91 - 6.9	40/20/40	1	7	20
6.91 - 9.2	60/10/30	3	7	24
9.21 - 13.1	70/10/20	4	12	31
13.11 - 22.8	80/10/10	5	20	41
22.81 - 100	90/10/0	6	41	-

From: Walter RB, Othus M, Borthakur G, Ravandi F, Cortes JE, Pierce SA, APpelbaum FR, Kantarjian HM< Estey EH. Prediction of early death after induction therapy for newly diagnosed acute myeloid leukemia with pretreatment risk socres: a novel paradigm for treatment assignment. *J Clin Oncol.* 2011;29(33):4417-4424.
